Data Analysis Behavioral Measures: The same general framework as those described for the R21 phase were used. We use univariate and multivariate mixed effects models (LMMs) to assess the effects of the VR intervention relative to the control game condition on the social assessment and symptom measures and other measures noted above (see below for fMRI). We assess effects both at post-Intervention for the VR condition and compare them with the post-intervention after the active control condition. As described in the R21 phase, we will also conduct intensive analyses within the VR condition of the trajectory of performance across 8 sessions of the social skills training. Using structural equation modelling approaches that are appropriate for the moderate sample size, we will further conduct mediational analyses assessing the important question of whether changes in social attention and in the trajectory of performance during training mediate the effects of treatment on social functioning and symptoms. As in the R21 phase, we will also compare post-treatment SZ to normative distributions, and model drop-out and attrition.

Neuroimaging data: VR task provides extensive opportunities to exercise social attention and simulation. We will examine the activity of the pSTS, IPL, and IFG in relation to social attention and social functioning. Our past work indicates that action imitation and simulation deficits in SZ but repeated practice improve performance. Furthermore, a recent study showed

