that simulation work exercises in VR significantly improved work function in real life. We will examine resting state functional connectivity data in relation to the primary outcome measures. Data Acquisition: A Philips Intera Achieva 3T scanner is used to collect high-resolution T1 anatomical images (170 slices; 1x1x1 mm), and T2\*-weighted functional images parallel to the AC-PC line (gradient-echo T2\*-weighted EPI; 25 slices; TR=2000ms; TE=35ms, flip angle=79°; FOV=240x240mm^2; voxel size =1.875x1.875x5mm^3). FMRI data analysis: BrainVoyager QX1.1 is used. Anatomical volumes are transformed into a common stereotactic space, and functional volumes for each subject are aligned to the transformed anatomical volumes. Standard pre-processing is performed: temporal high-pass temporal frequency filtering, linear de-trending, 3D motion correction, slice scan time correction, and spatial smoothing with a 6mm Gaussian kernel (full width half-maximum). Individual subject analyses are performed using a GLM with the 6 experimental conditions entered as regressors, and data are collapsed across runs. First, we compare SZ vs. CO at baseline to determine the integrity of the social brain network (group-by-instruction-by-stimulus type mixed-effects analysis) at resting state. Statistical maps are created for each group separately and for the group comparison. Multiple comparisons are corrected at p=.05 by Monte Carlo simulations to arrive at a cluster threshold. We will compare the pre- and post-treatment cortical activity patterns for each treatment regimen. We will also assess the relation between changes in activation of the social brain network and in social attention on the behavioral task and whether such changes predict changes on social outcome measures.

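### The fMRI plan specifies two task-based models, but the only functional scan it describes is a resting scan, on which neither can be fitted

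*Combined protocol and SAP*

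**What the plan says.** The R33 PROJECT DESIGN section lists a resting-state scan at baseline and again after the first 8 sessions. The final assessment after crossover is mentioned there without its contents. The Measures paragraph also names a resting-state scan at T1. The Procedure paragraph refers to fMRI at T1 without saying what kind.

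Under Neuroimaging data, two aims are given: "We will examine the activity of the pSTS, IPL, and IFG in relation to social attention and social functioning" and "We will examine resting state functional connectivity data in relation to the primary outcome measures".

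The FMRI data analysis text then sets out the models:

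- Subject level: "Individual subject analyses are performed using a GLM with the 6 experimental conditions entered as regressors, and data are collapsed across runs".
- Baseline SZ versus CO: "group-by-instruction-by-stimulus type mixed-effects analysis) at resting state".
- Output of that comparison: "Statistical maps are created for each group separately and for the group comparison".
- Error control, stated without sidedness or a cluster-forming threshold: "Multiple comparisons are corrected at p=.05 by Monte Carlo simulations to arrive at a cluster threshold".
- Treatment: "We will compare the pre- and post-treatment cortical activity patterns for each treatment regimen".
- Association: "We will also assess the relation between changes in activation of the social brain network and in social attention on the behavioral task", together with whether such changes predict social outcomes.

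**The concern.** The scan and the models do not match. A GLM with experimental-condition regressors, pooled over runs, analyses a task experiment. So does a factorial model in instruction and stimulus type. Neither has anything to work on when the participant is simply at rest.

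The neural part of aim 2 is at stake: the Study Protocol section makes neural change after the VR intervention one of the things to be compared with the control game. If the only stated subject-level imaging estimate cannot be produced, the measure, regions and model that replace it are left to whoever runs the analysis. The Age range paragraph already describes the recruited sample in the past tense, so that choice could be made with data in hand.

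**Working it through.** No arithmetic applies, because the plan gives no figure that bears on this point. The check sets the scan described beside the models stated.

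**1. What is acquired.** Every place that names a functional scan type (R33 PROJECT DESIGN, Measures, and the connectivity sentence under Neuroimaging data) says resting state. The Data Acquisition text gives sequence parameters only. Nowhere is there an in-scanner task, a list of conditions, a set of instructions or stimuli, event timing or a number of runs.

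**2. Subject-level GLM.** A condition regressor is built from the onsets and durations of events. A resting scan as described has none, so the 6 columns cannot be constructed and no condition effect can be estimated.

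**3. Baseline group model.** Of its three factors, only group (SZ, CO) has levels in a resting scan. Instruction and stimulus type have none, so their main effects and every interaction are undefined. The wording quoted under what the plan says contradicts itself within one sentence. The group maps and cluster correction follow from this comparison and cannot be produced as written.

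**4. Other readings of the 6 conditions.**

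- *Two training conditions by three assessment times.* This does not fit. The regressors sit inside each individual's GLM, controls are assessed at baseline only, and the factors named are instruction and stimulus type.
- *A task defined in the R21 phase.* R21 is invoked for the VR procedure and dose and for the behavioural analysis framework, not for imaging.
- *The behavioural task mentioned in the association analysis.* It supplies a social attention score and is not placed in the scanner.
- *A crossing of instruction and stimulus type.* Six is 2 × 3, so this would fit, but no such task is described.

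**5. Consequences for the remaining imaging analyses.** The pre/post comparison of cortical activity, the change-in-activation analysis and the pSTS/IPL/IFG activity analysis are not impossible in themselves, but the GLM is the only subject-level input defined for them. The connectivity aim can be run on a resting scan, but it has no stated measure, seed or region definition, or model. The pre-processing list includes motion correction but no nuisance regression.

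**6. Which treatment comparison a replacement should use.** No washout is stated between conditions, and training effects may persist. Write τ for the VR-minus-control effect, and λ_V and λ_C for what each condition carries into the second period. The standard two-period estimate is half the difference between the two sequences in their period 1 minus period 2 contrasts:

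½[(τ − λ_V) − (−τ − λ_C)] = τ − ½(λ_V − λ_C)

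Period effects cancel; differential carry-over does not. In the extreme case of λ_V = τ and λ_C = 0, the estimate is τ/2. The first-period comparison is free of this bias.

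**The case against.** The best defence is that a task scan may exist and simply be undescribed. The documents do not expressly exclude one, and six conditions would fit two crossed factors. That part stands, so the claim is conditional: the two models cannot be fitted on the scan the documents describe. It does not rescue the text, because an undescribed task would still need describing and the resting-state label would still be wrong for that comparison.

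The second defence is proportion. This is a small pilot, aim 1 and the behavioural models are untouched, and the baseline SZ-versus-CO comparison is not the randomised contrast. This stands too, and it limits the severity.

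A reader might infer more than the documents support:

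- *That every imaging analysis is impossible.* Only two models are contradicted; the rest are under-specified.
- *That the text was carried over from a task study.* It reads that way, but nothing settles it.
- *That a false-positive rate can be attached, for instance for tests on pairs of the three named regions.* The plan states no such tests, and its maps do have a planned cluster correction.
- *That the imaging data have already been examined.* The documents show that recruitment has taken place, not that scans have been analysed.

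**Conclusion.** The concern holds in limited form. The subject-level GLM and the baseline factorial model cannot be fitted on the resting scan that the documents name. The activity and activation analyses therefore have no defined input, and the connectivity analysis has no defined measure. The damage is confined to the neural part of aim 2.

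There is no numeric size to report. This should be fixed, but it is not a fatal defect: a stricter grading would treat the imaging part of a feasibility pilot as if the whole trial rested on it. The conclusion assumes that the scan is as described, with no experimental events. If a task scan was acquired, the defect becomes an undescribed task and a wrong label, and the text must still change.

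**What to change.** Reconcile the scan description with the analysis text.

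**A. If only resting scans are acquired:**

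- Delete the 6-condition GLM and the instruction-by-stimulus model.
- Define one resting connectivity measure per person and scan among pSTS, IPL and IFG, for example the mean Fisher-z correlation across pairs, with motion nuisance regression.
- Use that measure for the T1 SZ-versus-CO comparison, the pre/post comparison and the association with outcomes. Reword the references to activity and activation to match.
- For the treatment effect on connectivity, make the randomised first-period comparison, adjusted for T1, the main analysis. Any two-period crossover model is secondary, with carry-over acknowledged.
- Keep the Monte Carlo cluster correction only if whole-brain maps are kept.

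**B. If a task scan is acquired:**

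- Describe the task, its 6 conditions and its runs.
- Remove the resting-state label from that comparison.
- Say which contrast feeds the activation analyses.
- Specify the resting connectivity analysis separately.

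In either case, date the revision, and label the imaging analyses post hoc if the data have already been examined.

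**Cost.** A text revision, plus re-processing of any scans already acquired (the documents do not say how many). Some high-motion scans may be lost; no motion data are given, so the number is unknown. The first-period comparison is less precise than a within-person crossover estimate, which is the price of avoiding carry-over bias.

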## **R33 PROJECT DESIGN**

This is a small pilot study to compare the outcome measures after the VR social skills training compared with an active control video game. Participants with schizophrenia (SZ) undergo training. Participants with schizophrenia are randomly assigned to the social skills VR condition or the active control condition at baseline. After completing all the baseline assessments including clinical symptoms ratings, social cognitive assessments, and resting state fMRI scan, participants are asked to visit the lab for 8 sessions (twice a week) to complete the VR training or the active control condition. After 8 sessions, there is a post-training assessment that includes symptoms ratings, social cognitive assessments and resting state fMRI scan. Then participants cross over to the other condition for 8 sessions, after which there is a final post-training assessment. Demographically matched control participants are recruited to obtain comparison data but they do not undergo any training. Research staff conducting clinical symptoms and social functions assessments are blind to the VR training or control condition assignment.

VR Condition: The same procedure as outlined in R21 phase with the determined optimal dose of 8 sessions administered over 4-5 weeks.

Active Control Condition: We control for the number of lab visits, duration of game playing and computer use in the active control group by administering a commercially available video games which do not require any simulated social interactions but instead, support cognition.

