Inclusion/exclusion criteria for schizophrenia group: Participants were recruited from outpatient day facilities in Nashville. DSM-5 criteria were used to diagnose SZ. Those with a history of head injury, substance abuse, neurological diseases (e.g., stroke, tumors), hormonal disorders (e.g. Cushing's disease) or IQ<85 will be excluded. All patients were taking antipsychotic medications. When someone is very psychotic, any social remediation training is not going to be effective. Recruiting outpatients who are stabilized on medication, allowed us to work with the population whose psychotic symptoms are partially in remission but are still experiencing significant social cognitive impairments. The range of symptoms scores of our outpatient sample in the past 14 years in Nashville is very comparable to the scores reported by other groups. The mean SAPS score of our SZ outpatients from the past 14 years was 15.34 (S.D.= 8.36) and the mean SANS was 23.71 (S.D.=14.73). These scores are almost identical to the published mean SAPS (16.8, s.d.=14.2) and SANS (23.0, s.d.=14.6) scores from the FBIRN consortium 143. For this R33 study, if the SAPS or SANS score is 1 s.d. above the mean of our typical outpatient sample (i.e. SAPS > 23; SANS > 38), we planned to place that patient on a wait list until his/her symptom scores fall within 1 s.d. of the mean. This additional precaution should be able to address potential concerns that psychotic individuals may be adversely affected by virtual reality video games. (See below). One note of concern is the potential adverse effects of the COVID pandemic. This study was on hold for 2 years during the pandemic because we were unable to open the lab to test and train participants due to the concerns of infection. After the study was able to start in 2021, we noted worsening of physical health of the SZ individuals who had consented to participate prior to the pandemic.

Inclusion/exclusion criteria for the healthy control group: Healthy participants were recruited from the Vanderbilt University web-based recruitment panel and from Nashville Metro area via signs placed in public buildings (e.g. supermarkets, Laundromats, gyms, cafes). Exclusion criteria were: Axis I psychotic disorders in themselves or their families (e.g. schizophrenia, bipolar disorder), history of head injury, substance abuse, neurological diseases (e.g., stroke, tumors), hormonal disorders (e.g. Cushing's disease) and IQ<85.

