Additional screening for neuroimaging in R33: There are further exclusion criteria for fMRI in the R33 phase because those at primary risk from exposure to high-intensity magnetic fields must be excluded. Exclusion criteria are implanted medical devices (e.g. pacemakers, cochlear implants, IUDs), implanted paramagnetic prostheses, and augmentations (e.g. steel pin). People at secondary risk are also excluded (e.g. asthma, heart disease, diabetes etc). Potential participants must fill out the standard questionnaire used with all patients undergoing MRI at the Vanderbilt University Medical Center. If a potential participant meets the criteria for inclusion in the fMRI component, he/she will go through the informed consent procedure for neuroimaging. If a participant does not meet the inclusion criteria for fMRI part, he/she will not participate in the neuroimaging but will participate in all other parts provided that he/she meets the inclusion/exclusion criteria described above.

Age range: Included age range was 18 and 65. In our actual recruited sample the youngest participant was 20. Aging increases the likelihood of introducing confounding factors such as cognitive decline, dementia, hormonal changes and others. This age group will be

familiar with video games and computers. This is important because the VR training and active control training are similar to video games.

**Ethnic composition and diversity**: Nashville metropolitan area is increasingly ethnically diverse. We tried to recruit ethnically representative samples of SZ and CO. In our past studies in Nashville, about 20% of our participants were African-Americans.

Gender: We aimed to recruit 50% women.

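### The baseline patient-versus-control imaging model has no demographic term, although controls are matched and MRI-only exclusions may disturb the match among those scanned

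*Combined protocol and SAP*

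**What the plan says.** R33 PROJECT DESIGN describes the comparison group: "Demographically matched control participants are recruited to obtain comparison data but they do not undergo any training". It names no matching variables, ratio or method.

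The FMRI data analysis text under Neuroimaging data gives the individual-level model, "Individual subject analyses are performed using a GLM with the 6 experimental conditions entered as regressors", and then the baseline group comparison, "First, we compare SZ vs. CO at baseline to determine the integrity of the social brain network (group-by-instruction-by-stimulus type mixed-effects analysis) at resting state". The only between-subject term is diagnosis. The mixed models under Data Analysis Behavioral Measures refer the reader elsewhere for fMRI, so they supply no missing covariate.

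Additional screening for neuroimaging in R33 adds criteria that apply to the scan alone. On primary risk: "Exclusion criteria are implanted medical devices (e.g. pacemakers, cochlear implants, IUDs". On secondary risk: "People at secondary risk are also excluded (e.g. asthma, heart disease, diabetes etc". Someone who fails them stays in the study: "he/she will not participate in the neuroimaging but will participate in all other parts". Diabetes is recorded, not excluded, in the general criteria, so this screen can remove enrolled people. No re-matching or balance check is stated for those scanned. The Procedure paragraph, however, says that every participant has fMRI at T1.

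On the patients' health after the pandemic pause, the schizophrenia criteria say: "we noted worsening of physical health of the SZ individuals who had consented to participate prior to the pandemic".

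**The concern.** Matching makes the two groups alike on the matched variables. It does not remove the variation that those variables cause within each group. If age or sex predicts connectivity and is left out of the model, that variation stays in the residual, and the standard error is larger than it need be. The eligible age range is 18 to 65, and the plan itself treats ageing as a source of confounding.

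The match is also made at recruitment, whereas the comparison uses those scanned. IUDs affect women only. I assume that heart disease and diabetes become more common with age. If these exclusions remove a different share or type of patients than of controls, the scanned groups can differ in age or sex, and a model with diagnosis alone would attribute that difference to diagnosis.

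At stake is the first imaging analysis listed, which is meant to establish how intact the patients' social brain network is before training. A true difference could be missed, or its size misjudged.

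**Working it through.** The documents give no sample size, effect size, SD or exclusion count for this comparison, so there is no figure to reproduce. All numerical inputs are assumptions except the age range and the 50% target for women.

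**Inputs.** 25 recruited per group; true difference d = 0.6 SD; two-sided 5% test; one regional outcome; age-outcome correlation r = 0, 0.3 or 0.5, so R² = r² = 0, 0.09 or 0.25.

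**Step 1: precision, match intact.** Leaving out the covariate inflates the standard error by 1/√(1 − R²). That is 1/√0.91 = 1.048 at r = 0.3 and 1/√0.75 = 1.155 at r = 0.5. At R² = 0.02 it is only 1.01.

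Suppose 20% of each group is excluded, leaving 20 per group. Approximate power is Φ(0.6 / [√(2/20) · √(1 − R²)] − 1.96), with √(2/20) = 0.316. The simulation column uses t-based tests with both age and sex fitted and equal exclusions; it includes the cost of two degrees of freedom.

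| r | d / SE | Approximate power with covariate | Gain over 47.5% | Simulated change |
|---|---|---|---|---|
| 0 | 1.897 | 47.5% | 0 | about −1 point |
| 0.3 | 1.989 | 51.2% | 3.7 points | about +3 points |
| 0.5 | 2.191 | 59.1% | 11.6 points | about +11 points |

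**Step 2: can the exclusions disturb the match?** If a fraction f of a group is excluded, and those excluded are g SD older than those kept, the mean age of those kept falls by f·g. The imbalance between groups is (f_SZ − f_CO)·g.

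- 10% and 10%, same g: 0.
- 20% and 10%, g = 1: 0.1 SD.
- 30% and 10%, g = 1: 0.2 SD.

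For sex, start from 50% women. An IUD exclusion of 20% of control women and no patient women leaves 0.5 × 0.8 / (1 − 0.5 × 0.2) = 44.4% women among controls, against 50% among patients. If 10% of women are excluded in both groups, each has 47.4% and there is no imbalance. Only unequal exclusion matters.

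**Step 3: bias.** Bias = imbalance × r. With 0.2 SD it is 0.06 SD at r = 0.3 and 0.10 SD at r = 0.5.

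A simulation with exclusion rising with age and heavier in patients gives about 0.05 and 0.08 SD. Assumptions of this kind are exclusion rising from 10% to 50–70% in patients and from 3–5% to 15–20% in controls, leaving about 15 to 17 patients and 22 controls. Relative to 0.6 SD, the bias is 0.05/0.6 = 8% and 0.08/0.6 = 13%. If the outcome worsens with age and the scanned patients are younger, it shrinks the apparent deficit. Adding age and sex removes it and raises power by about 9 and 21 points.

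**Step 4: false positives.** A 0.25 SD imbalance at r = 0.3 gives a bias of 0.075 SD, or 0.075/0.316 = 0.24 standard errors at 20 per group. By a normal approximation that ignores any remaining match, the false-positive rate is about 5.6%. With the match intact the unadjusted test is conservative: about 2.5% at r = 0.5. The likelier harm is a missed difference.

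**The case against.** A reader might infer that the MRI exclusions undo the match. The documents do not show this. The criteria are worded for all potential participants, no counts are given, and the remark on worsening health is unquantified, concerns patients who consented before the pandemic and says nothing about MRI eligibility. The Procedure paragraph even implies that there is no separate scanned subset. What stands is that the match may be disturbed, and that nothing in the plan would detect or correct it.

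A reader might also treat the controls as one-to-one pairs and quote a much larger loss. With 20 pairs, d = 0.6 and a within-pair correlation of 0.5, an independent-samples test has 44% power against 72% for a paired test. Pairing is not stated, and neither age nor sex is named as a matching variable. If pairs are alike only on the matched variables, their correlation is roughly R². A value of 0.5 then needs a multiple correlation of √0.5 = 0.71, whereas r of 0.3 to 0.5 gives 0.09 to 0.25. Those figures should not carry the point.

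The label "group-by-instruction-by-stimulus type mixed-effects analysis" belongs to a task design and does not fit a resting scan, so it may not be the model finally fitted. That is a fair and separate defect. It does not answer this one, because no between-subject demographic term is stated for any version of the comparison.

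Lastly, the contrast is secondary. The aims are feasibility and VR against the active control. Controls are assessed only at baseline, and the before-and-after comparisons by regimen are within patients. This limits the importance of the point and stands.

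**Conclusion.** The point holds in a moderate form. The plan matches controls demographically, states an SZ-versus-CO imaging model without any demographic term, and lets MRI-only exclusions define the scanned set without a check on balance.

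The precision cost does not need unequal exclusion, but it does need age or sex to predict the outcome. It ranges from nothing at r = 0 to about 11 points of power at r = 0.5. Confounding needs unequal exclusion as well, and under the fairly heavy rates assumed it stays below 0.1 SD. The documents establish neither the correlations nor the exclusion rates, so these sizes are illustrations and not estimates for this trial.

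It would be wrong to conclude that the randomised comparison of VR with the control game is compromised. The healthy controls play no part in it. The change is worth making because it is almost free, not because the main result depends on it.

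**What to change.** In the FMRI data analysis text, add age and sex as between-subject covariates to the baseline SZ-versus-CO model and to the group-comparison map, fitted to the participants actually scanned. Word this so that it applies to whatever resting-state outcome is finally modelled.

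In R33 PROJECT DESIGN, name the matching variables and the method. If controls were matched one-to-one, repeat the comparison on intact scanned pairs with a pair term, as a sensitivity analysis. Report age and sex of scanned participants by group, with the number excluded from MRI in each.

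Reconcile the Procedure paragraph, under which everyone has fMRI at T1, with Additional screening for neuroimaging in R33, under which some do not.

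The cost is a few sentences and two error degrees of freedom, about 1 point of power if age and sex do not predict the outcome. No new participants, visits or scans are needed.

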## **Study Protocol**

We were able to show the target engagement in the R21 phase of this study. The major goal of the R33 phase is to prepare for a future randomized controlled clinical trial (RCT) by piloting a feasibility study that includes an active control arm and multimodal pre- and post-treatment measures. We aimed to achieve the following: (1) test the feasibility of recruiting, randomizing and retaining patients for VR social skills training; 2) compare the social skills training VR compared an active control VR game by measuring behavioral and neural changes after VR intervention.

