Procedure: All participants undergo baseline assessments at T1, including fMRI. The research staff conducting assessments are blind to the treatment groups and those who supervise the training session do not do assessments. SZ play the VR game or active control game in the lab. The VR dosing was determined in the R21 phase (8 sessions). After the completion of the training, they are given the post-training assessments and then switch over to the other condition for 8 sessions. We use the same dose for the active control condition. The VR and control game performance scores are saved at each session. To boost adherence, we text 1 day before and 2 hours before the visit. Subjects are paid per session and receive a small bonus at the end of the training. An exit interview is conducted to find out about acceptability and engagement.

Measures: At baseline (T1), we assess social cognitive functions, symptoms and conduct a resting state fMRI scan. To elucidate the mechanism of change, we focus on the social attention and the integrity of the social brain network that supports social cognition. Training begins within a week of completing the assessments. Within a week of the completion of the training, we conduct post-treatment assessments. Next, SZ participants cross over to the other condition and complete 8 sessions, after which they undergo another post-training assessments. Control participants complete only the baseline assessments.

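### Aim 2 includes VR versus active control on neural change, but the imaging analysis specifies only pre/post changes within each regimen and no contrast between regimens

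*Combined protocol and SAP*

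**What the plan says.** The opening Study Protocol section sets the second aim: "compare the social skills training VR compared an active control VR game by measuring behavioral and neural changes after VR intervention". Under R33 PROJECT DESIGN, patients are randomised to one condition and scanned at baseline. The section continues: "After 8 sessions, there is a post-training assessment that includes symptoms ratings, social cognitive assessments and resting state fMRI scan". It then says: "Then participants cross over to the other condition for 8 sessions, after which there is a final post-training assessment". The content of that final assessment is not itemised. The Measures paragraph repeats the switch ("Next, SZ participants cross over to the other condition and complete 8 sessions"), and neither section states a washout.

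The paragraph Data Analysis Behavioral Measures plans mixed models of VR against the control game on "social assessment and symptom measures and other measures noted above (see below for fMRI"). Its next sentence compares assessments after VR with assessments after the control condition.

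The imaging text that follows contains five analyses:

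- "We will examine the activity of the pSTS, IPL, and IFG in relation to social attention and social functioning";
- resting connectivity in relation to the primary outcomes;
- patients against healthy controls at baseline;
- "We will compare the pre- and post-treatment cortical activity patterns for each treatment regimen";
- relations between changes in activation, social attention and social outcomes.

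**The concern.** Only the fourth of the five imaging analyses concerns treatment, and it is worded within regimen. No difference in changes, regimen-by-time term or post-VR against post-control imaging contrast is written down.

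A within-regimen change mixes the effect of the regimen with anything else that moves between scans, such as time and familiarity with scanning. The active control is there to remove such non-specific change, and the stated imaging comparison does not use it. Nor can two separate significance results stand in for a comparison. If both regimens have the same true change and the two tests are independent, exactly one is significant with probability 2 × power × (1 − power): 42%, 50% or 32% at power 0.30, 0.50 or 0.80 (assumed values). A neural advantage of VR could be reported where there is none.

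**Working it through.** The documents give no imaging sample size, effect, carryover or repeat-scan figure, so there is no stated figure to reproduce. The check is algebraic, and the inputs are assumptions.

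**Model.** V and C are the true effects of VR and control, L is the share of the first effect still present at the final scan, and p is the change per period common to both regimens. T1 is set to 0 and the two orders are of equal size.

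- VR first: first post-training scan V + p; final scan LV + C + 2p.
- Control first: first post-training scan C + p; final scan LC + V + 2p.

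**Within-regimen changes.** The text leaves three readings open:

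| Reading | VR change | Control change | Difference |
|---|---|---|---|
| No final scan | V + p | C + p | V − C |
| First post-training scan is the second regimen's baseline | V − (1−L)C/2 + p | C − (1−L)V/2 + p | (V−C)(3−L)/2 |
| T1 is the baseline for both | V + LC/2 + 1.5p | C + LV/2 + 1.5p | (V−C)(1−L/2) |

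**Numbers.** Take V = 0.5, C = 0.1 and p = 0.2 scan SDs, so the true difference is 0.40.

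- No final scan: 0.70 − 0.30 = 0.40.
- First post-training scan as baseline: 0.70 − 0.30 = 0.40 at L = 1, and 0.65 − 0.05 = 0.60 at L = 0.
- T1 as baseline for both: 0.80 − 0.40 = 0.40 at L = 0, and 0.85 − 0.65 = 0.20 at L = 1.

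With V = C = 0, the VR change on its own is still p = 0.20 under the first two readings, and 1.5p = 0.30 under the third. In no reading is it zero.

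**Randomised contrast at the first post-training scan.** (V + p) − (C + p) = V − C whatever L and p are: 0.40 in the example and 0.00 when V = C = 0. A simulation (20,000 trials, n = 40, correlation 0.6) gave 0.401, 0.399 and 0.400 at L = 0, 0.5 and 1 for this contrast adjusted for T1.

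**Precision.** With scan SD 1, scan-rescan correlation ρ and n scanned patients split equally, SE = √(4(1−ρ²)/n) and half-width = t(0.975, n−3) × SE. For n = 20 and ρ = 0.5, SE = √(3/20) = 0.387, and 2.11 × 0.387 = 0.82.

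| Scanned patients (assumed) | Half-width, ρ = 0.5 | Half-width, ρ = 0.7 |
|---|---|---|
| 20 | 0.82 | 0.67 |
| 40 | 0.55 | 0.46 |
| 60 | 0.45 | 0.37 |

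**The case against.** The best defence is that the behavioural paragraph already covers imaging. The resting-state scan is listed under Measures, so it may be among the other measures the mixed model takes in. The pointer to fMRI may only promise further detail, and the next sentence does compare the two conditions. This stands in part: a regimen comparison may well be intended, and a reader who inferred that the plan rules one out, or cannot deliver one, would go too far. But the paragraph is headed as behavioural, and the text it points to states no contrast. Even on the generous reading, the imaging estimate is left unspecified.

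A reader might also infer that subtracting the two planned changes inflates the VR advantage by up to 1.5 times. The documents do not support that as a general statement. It holds only if a final scan is taken, the first post-training scan is the second regimen's baseline, and the first effect has gone. With no final scan there is no distortion, and with T1 as baseline for both the difference is attenuated, down to half at L = 1.

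Two practical objections stand. The half-width exceeds the illustrative difference of 0.40 in five of the six cases tabulated. And this is a small pilot whose major goal is to prepare for a later trial, with imaging in a mechanistic role. Both argue for an exploratory estimate and modest severity, not for leaving the contrast out.

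**Conclusion.** The concern holds as a gap in specification. Aim 2 calls for VR against control on neural change, and the imaging text specifies only the change within each regimen. As written, each change carries the full common time and repeat-scan component, so the neural part of the aim has no specified estimate. That conclusion rests on the wording and needs none of the assumed values. The size of any carryover distortion cannot be stated until the second regimen's baseline scan is defined and it is clear whether a final scan is taken; across the three readings the subtracted difference runs from 0.5 to 1.5 times the true one. The first-period contrast avoids that dependence, given randomised order and provided that missing scans do not differ by order in a way related to outcome. Low to moderate severity: a cheap improvement to a feasibility pilot.

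**What to change.** Add to the FMRI data analysis text:

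> *The VR-minus-control difference in the resting-state measure for pSTS, IPL and IFG will be estimated with a 95% CI, as an exploratory analysis, by comparing the first post-training scan between the randomised orders, adjusted for the T1 scan. If a final scan is taken, a two-period model with regimen, period and sequence terms will also be reported, with its dependence on carryover stated. Within-regimen pre/post maps are descriptive.*

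State also whether the final assessment includes a scan, and which scan serves as the second regimen's baseline.

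The cost is a few lines of text and one estimate per region. The main contrast needs no new scans, because fMRI is already itemised at baseline and at the first post-training assessment. The downside is a wide interval, since anyone who fails MRI screening "he/she will not participate in the neuroimaging but will participate in all other parts". With an assumed 20 scanned patients the half-width is about 0.67 to 0.82 SD, and Bonferroni intervals over the three regions would be 23% to 26% wider (at 60 and 20 scanned patients). The two-period model uses more data, but it buys precision only through assumptions about carryover.
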